#### **2.9.4 Other analysis**

The concomitant medications, including those for study eye and fellow eye, will be grouped into those taken pre-randomization and those taken post-randomization as well as those taken post-treatment, based upon the starting dates of the concomitant medication and the treatment.

Number and percent of subjects in the safety population who take pre-randomization concomitant medications will be reported. Number and percent of subjects in the safety population who take post-randomization concomitant medications will be reported by treatment and by study eye vs. fellow eye. Number and percent of subjects in the safety population who take post-treatment concomitant medications will be reported by treatment and by study eye vs. fellow eye.

### 3 STUDY POPULATION

#### 3.1 Definition of Subject Populations

All subjects who have the randomization procedure completed at Day 1 are considered study participants or Randomized Population. The following subject populations are defined to assess the safety and efficacy of AG-920 in comparison with Proparacaine.

##### Safety Population

The safety population is defined as all subjects who are randomized and who have received at least one drop of the dose (2 drops) of study medication. The safety population will be utilized for comparative safety analyses among treatment groups.

##### Intention-to-treat (ITT) Population

This population is defined as all subjects who are randomized to treatment and have received at least one dose (2 drops) of the study medication. The ITT population is the primary population for efficacy evaluation in this study. Treatment identification is defined in the ITT population by treatment assignment. The ITT population will be identified and finalized before the database is locked and the treatment assignment is merged into the study database.

##### Per-Protocol (PP) Population

This population is defined as a sub-population of the ITT population. The PP population is the secondary population for efficacy evaluation in this study and will be defined as all randomized subjects who completed the study treatment with no major protocol violations likely to seriously affect the primary outcome of the study as judged by the investigator. In case there is a difference between treatment assigned and received, treatment actually received will be utilized to define the treatment identification in the PP population. In case there are missing data in efficacy measures, the analysis of the PP population will be based on observed or actual data only (without imputation). The PP population will be identified and finalized before the database is locked.

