### 3.5 Randomization and procedure for breaking the code

A randomization code for allocating the treatments and study eye will be prepared by an independent biostatistician, who is not involved in the day-to-day conduct of the study. Subjects

will be randomized in a 1:1 ratio to receive AG-920 or Proparacaine HCl Ophthalmic Solution. The site will have a randomization list that will assign each subject to treatment and study eye.

The study is single masked. Treatment assignments will be masked to the subjects and their parent/legal guardian only so there is no reason to break the code.

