### 9.3 *Analysis populations*

Randomized Population: The randomized population will include all subjects who were randomized to treatment. Baseline (screening) variables and demographic characteristics will be summarized for this population.

Intent-to-Treat Population (ITT): The ITT population will include all randomized subjects who have received at least one dose (two drops) of study medication. This population will be the primary population for the efficacy analyses and all efficacy variables will be summarized using this set of subjects. The ITT population will include subjects as randomized.

Per-protocol population (PP): The PP population is a subset of the ITT population, which will include those subjects (and their visits) who do not have major protocol violations likely to seriously affect the primary outcome of the study as judged by a masked evaluation prior to the unmasking of the study treatment. This population will be the secondary population for efficacy analyses and all efficacy variables will be summarized using this set of subjects. If the PP and ITT populations are exactly the same and there are no missing data, then additional efficacy analyses on the PP population will not be performed. The PP population will include subjects as treated.

Safety Population: The safety population will include all randomized subjects who have received at least one drop of study medication. This population will be used to summarize the safety variables and will summarize subjects as treated.

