### 2.2 Description of Trial Design

This is a Phase 3, randomized, active-controlled, single-masked, parallel-group study of safety and anesthetic efficacy of AG-920 topical drop versus Proparacaine HCl Ophthalmic Solution (Proparacaine) in healthy pediatric subjects. The study will evaluate the safety and anesthetic efficacy following one dose of Articaine Sterile Topical Ophthalmic Solution (AG-920), in comparison with Proparacaine (active-control). Eligible subjects will be randomized in a 1:1 ratio to receive a single dose of AG-920 or active-control into one eye, designated as subject's study eye. The application of one single dose of AG-920 or active control involves two drops of the study medication 30 seconds apart into the subject's study eye.

The study consists of two visits and a follow-up phone call: one screening visit on Day -2 (Visit 1), one baseline/assessment visit on Day 1 (Visit 2), and one follow-up phone assessment on Day 2-5 (Phone Follow-Up). The screening visit and baseline/assessment visit may be conducted on a single day.

Following the screening visit, eligible subjects will return to the clinic on Day 1 to have their study eye randomly assigned (right eye=OD or left eye=OS) and to be randomized to receive the study medication into the study eye. Two to four minutes post the end of their dose (following second drop), subjects will undergo an eye exam for which the subject is seeing the ophthalmologist and the principal investigator (PI) will assess if they were able to conduct the eye exam or not. Dosing of the study medication and eye exam will be performed by the PI.

To assess the anesthetic effect of the study medication, PI will be queried if the subject has achieved adequate anesthesia for the PI to conduct the eye exam at 2 to 4 minutes post dose application by answering Yes or No. 15 to 60 minutes post dose application, the following eye exam or tests will be performed by the PI: visual acuity and external eye exam and, if needed, a slit lamp bio-microscopy test.

All subjects who are randomized and who receive a single dose of either AG-920 or Proparacaine HCl Ophthalmic Solution on Day 1 will be followed up with a phone call on Day 2-5 (1-4 days post treatment) for safety assessment.

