### 2.4 Randomization

As stated in the protocol, a randomization schedule generated by the Sponsor or designee will be used to assign subjects to each of the two treatment groups with a 1:1 allocation ratio to receive a single dose of AG-920 or Proparacaine according to the randomization schedule.

Study medication will be packaged with an investigational label. Marketed Proparacaine HCl Ophthalmic Solution will be "overwrapped" with an investigational label.

[REDACTED]

[REDACTED]

[REDACTED]

Each eligible subject will be assigned to one of the prepackaged packs available at a site. The study is single masked. Treatment assignments and study medication will be masked to the subjects and their parent/legal guardian only. The treatment randomization number or study medication kit number assigned to the subject will be recorded on the CRF at the site.

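### SAP 3.1 gives per-protocol exclusions to the investigator, who is not masked, where Protocol 9.3 requires a masked evaluation

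*SAP*

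**What the plan says.** **Who decides on PP exclusions.** Protocol 9.3 has major violations judged as follows: "as judged by a masked evaluation prior to the unmasking of the study treatment". Protocol 9.4.5 agrees, since important deviations are to be settled before unmasking. SAP 3.1 admits subjects "with no major protocol violations likely to seriously affect the primary outcome of the study as judged by the investigator" and states no masking condition.

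**When the sets are fixed.** For ITT, SAP 3.1 says: "The ITT population will be identified and finalized before the database is locked and the treatment assignment is merged into the study database". For PP it says only: "The PP population will be identified and finalized before the database is locked".

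**Who is masked.** SAP 2.4: "Treatment assignments and study medication will be masked to the subjects and their parent/legal guardian only". Protocol 3.5 says the same: "Treatment assignments will be masked to the subjects and their parent/legal guardian only so there is no reason to break the code". It adds: "The site will have a randomization list that will assign each subject to treatment and study eye".

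**Who supplies the outcome.** Protocol 7 and SAP 2.6 make the sole efficacy endpoint the investigator's own YES/NO on whether anesthesia was adequate for the eye exam. SAP 2.6.2 defines no secondary efficacy endpoint.

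**What PP is for.** Protocol 9.4.6 repeats the ITT analysis in PP as a check of robustness. Both documents call PP the secondary efficacy population.

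**Who doses.** SAP 2.2: "Dosing of the study medication and eye exam will be performed by the PI". Protocol 3.1 and 5 give dosing to study or clinic staff.

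**The concern.** A PP analysis supports the ITT result only if the exclusions were chosen without regard to treatment arm and outcome. Under the protocol's rule they are. Under the SAP's rule, the person who decides whether a violation was serious enough to affect the primary outcome can know the arm and has already given the answer. Requiring the list before database lock does not help, because lock does not hide anything from someone who already knows the assignment. The ITT wording, which adds the merge of treatment assignment, shows that the SAP's authors had the safeguard in mind and did not carry it to PP.

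At stake is the evidential value of agreement between PP and ITT. The trial claims equivalence from a non-significant P value (Protocol 9.4.6, SAP 2.9.1) and from a 90% confidence interval within 20% of the reference (SAP 2.9.1). With about 30 evaluable subjects per arm, either criterion can turn on one subject.

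**Working it through.** **Step 1: the texts.**

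| Item | Protocol | SAP |
|---|---|---|
| Judge of PP exclusions | Masked evaluation (9.3) | The investigator (3.1) |
| Timing | Before unmasking (9.3, 9.4.5) | Before database lock (3.1, PP) |
| Timing for ITT, for contrast | Not stated | Before lock and before assignment is merged (3.1, ITT) |
| Masked parties | Subject and parent or guardian only (3.5) | The same (2.4) |

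That the investigator is unmasked is an inference, but a firm one: masking is confined to subject and parent, and the site holds the list. The first row is a direct contradiction that no other passage resolves.

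**Step 2: inputs for scale.** The plan has no figure to reproduce here. The sample size is attributed to the FDA's direction, and no response rates are given. From the documents: about 30 evaluable subjects per arm (Protocol Summary), two-sided 0.05 (Protocol 9.1), Pearson chi-square (Protocol 9.4.6), and a 90% CI from an ANOVA with a 20% margin (SAP 2.9.1). Assumed: the counts of YES answers. They were picked near the decision boundary to show what one exclusion can do, not how often it would.

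**Step 3: formulas.** With a/n1 YES on AG-920 and b/n2 on Proparacaine, N = n1 + n2:

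- Pearson chi-square without continuity correction = N[a(n2-b) - b(n1-a)]² / [n1·n2·(a+b)·(N-a-b)], 1 df.
- d = a/n1 - b/n2. Residual variance s² = [a(n1-a)/n1 + b(n2-b)/n2] / (N-2). SE = √[s²(1/n1 + 1/n2)]. The 90% CI is d ± t(0.95; N-2)·SE. The eye-side term is left out here and restored in step 5.

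**Step 4: results.**

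*ITT, 26/30 vs 30/30.* Chi-square = 60·120²/(30·30·56·4) = 4.286, P = 0.038. d = -13.3 points, s² = 3.467/58 = 0.0598, SE = 6.31 points, t = 1.672. The 90% CI is -23.9 to -2.8 points. Neither rule is met.

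*PP after excluding one AG-920 NO, 26/29 vs 30/30.* Chi-square = 59·90²/(29·30·56·3) = 3.270, P = 0.071. d = -10.3 points, s² = 2.690/57 = 0.0472, SE = 5.66 points, t = 1.672. The 90% CI is -19.8 to -0.9 points. P exceeds 0.05 and the interval lies within ±20 points.

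*Almost all YES, 29/30 vs 30/30.* P = 0.313, lower limit -8.9 points. ITT already meets both rules, and excluding the one NO changes neither verdict.

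**Step 5: check with the SAP's own methods.** I used CMH by eye side and two-way ANOVA, assumed 15 subjects per eye side and arm before exclusion, and ran every split of the NO answers. For 26/30 vs 30/30, P is 0.035 to 0.042 and the lower limit -24.0 to -23.6. For 26/29 vs 30/30, P is 0.063 to 0.076 and the lower limit -19.9 to -19.5. The verdicts are the same. Reading the 20% as relative to the reference changes nothing here, since 20% of 100% is 20 points.

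Protocol 9.4.6 also wants the difference to be around zero. It attaches no number to that, so the condition is not modelled.

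**The case against.** The best defence has four parts.

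*PP is secondary.* This stands. SAP 2.9.1 runs the primary analysis on ITT, so a PP exclusion cannot change the primary equivalence verdict. A reader might infer that the trial's main claim is exposed; the documents do not support that.

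*Discretion is narrow and visible.* Only major violations count, and Protocol 9.4.5 says deviation criteria will be defined in another document. The PP analysis is skipped if PP equals ITT and nothing is missing (Protocol 9.3). SAP 3.7 lists ITT subjects left out of PP (Listing 5), and SAP 4.5.1 lists each ITT subject's answer by treatment (Listing 6). This stands in part: exclusions could be inspected afterwards, but visibility does not mask the choice when it is made.

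*The trial is single-masked by design.* This is true, disclosed and consistent across both documents, and it is not an error. It does not answer the point, because the protocol accepts an unmasked site and still asks for a masked PP evaluation.

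*The example is chosen at the boundary.* This stands. The PP lower limit of -19.8 only just clears -20, and the counts are assumed.

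Two further inferences are tempting. One is that SAP 2.2, by having the PI dose, biases the primary answer. The PI can know the arm under the protocol's wording too, study staff could include the PI, and no added bias from that sentence can be shown. The other is that Protocol 5.1.2 makes the Sponsor a further judge of PP membership. That passage concerns medication questions and inclusion of later visits, and it does not mention PP.

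**Conclusion.** The contradiction over who judges PP exclusions is real, and the SAP's version is the weaker safeguard. Its effect is confined to the secondary PP analysis: agreement between PP and ITT would be less convincing, because the PP set could be chosen by someone who can know the arm and who gave the answer. In the assumed example, one exclusion makes PP meet the P > 0.05 rule and the ±20-point rule when ITT meets neither. This shows what is possible and does not estimate how likely it is. It rests on 30 per arm, counts near the boundary and an unquantified around-zero condition. With near-universal YES answers the practical effect is close to nil.

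The difference over who doses is a minor inconsistency of wording. The passages must be reconciled, and no view is taken here on who should dose.

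**What to change.** 1. In SAP 3.1, replace the investigator's judgement with a masked evaluation, as in Protocol 9.3, made by people without access to treatment assignment. The protocol does not say who they are, so the SAP should name the function. The investigator still reports the facts of each deviation.
2. In the same section, require the PP list to be final before database lock and before treatment assignment is merged, as already stated for ITT.
3. Reconcile SAP 2.2 with Protocol 3.1 and 5 on who doses.

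Items 1 and 2 are changes of wording in one SAP section. They need no new data and no change to the endpoint, sample size or primary analysis. The cost is that someone without access to assignment must carry out the review, which the protocol already requires. The change should be made before the PP set is decided, because a set chosen with knowledge of the arm cannot later be shown to be free of that knowledge. Item 3 is a sentence in one document or the other.

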#### 3.2 Screening and Enrollment

A screening summary including the number of subjects screened for study participation will be presented by site ([Table 1.1.1](#)).

An enrollment summary including the number of subjects enrolled/randomized, treated, and completing the study will be presented for all enrolled subjects and by site ([Table 1.1.2](#)). Enrolled subjects include those individuals who are screened and randomized into the study. The number of subjects treated with at least one drop of the dose of the study medication (i.e., the safety population) will be summarized for each treatment group and overall ([Table 1.1.3](#)). The number of subjects treated with at least one dose (2 drops) of the study medication (i.e., the ITT population) will be summarized for each treatment group and overall ([Table 1.1.4](#)). The number of subjects in the PP population will be summarized for each treatment group and overall ([Table 1.1.5](#)).

### **3.3 Population Demography**

For subjects enrolled, safety, ITT, and PP populations, descriptive summaries of demography and baseline characteristics will be presented for each subject group and overall to establish baseline comparability (Tables 1.2.1 to 1.2.4).

Demography includes age in years (continuous and categorical 5-, 6 to 8, 9 to 10, and 11+), gender, race, and ethnicity. Demography will also be listed for all subjects enrolled (Listing 1).

### **3.4 Disease Characteristics and Prior Treatment**

For the safety, ITT and PP populations, descriptive summaries of baseline study eye characteristics will be presented for each treatment group and overall to establish baseline comparability (Tables 1.3.1 to 1.3.3).

Visual acuity and other characteristics of the study and fellow eye will be listed for all subjects enrolled (Listing 1).

### **3.5 Medical History**

Medical history will be listed in listing and CRF data tabulation.

### **3.6 Disposition of Study Participants**

Subject disposition including completion and discontinuation along with CRF-based termination reason will be summarized for safety and ITT populations (Tables 1.4.1 to 1.4.2). Subjects' early termination details will be listed for all subjects enrolled (Listing 2).

Subjects' randomized treatment, randomization (or kit) number, and randomization date as well as actual treatment received will be listed for all subjects randomized (Listing 3).

### **3.7 Protocol Deviations and Violations**

A summary of protocol deviation and violations will be provided for the ITT population (Table 1.5.1). Subjects who are randomized to receive single-masked treatment in the study and included in the ITT population but do not have two drops of IMP dosed and/or post-dose status of anesthetic effect assessment will be listed for subjects randomized (Listing 4).

Subjects who are included in the ITT population but not included in the PP population due to either protocol violations or other reasons will be listed for all subjects excluded from the PP population (Listing 5).

## **4 EFFICACY EVALUATION**

### **4.1 Datasets Analyzed**

The ITT population is defined as the primary efficacy population and the PP population as the secondary efficacy population. Both populations will be identified and finalized before the database is locked. The definitions of the two populations are provided in Section 3.1.

In addition, sub-population datasets may be defined as the ITT subjects in each gender group (male vs. female), each age group (8- vs. 9+), each racial group (Caucasian vs. Non-Caucasian), and each color of the eye iris (dark brown vs. other colors).

## 4.2 Treatment Compliance

The compliance rate during treatment will be summarized by treatment group and demographic parameters for the safety and ITT populations ([Tables 1.5.2](#) and [1.5.3](#)).

## 4.3 Data Missing and Imputation

A summary of the observed data missing and imputation performed will be reported for study eye anesthetic effect status, the primary efficacy measure of the ITT population in [Table 1.6.1](#).

## 4.4 Baseline Measures

Medical history will be listed for individual subjects. Descriptive statistics of the study eye characteristics will be presented in [Section 3.4](#).

## 4.5 Efficacy Results and Tabulations

### 4.5.1 Results of primary efficacy analysis

Descriptive and inferential statistics on the ITT population of the proportion of subjects with anesthetic effect assessed by the PI at 2 to 4 minutes post dose will be presented in [Table 2.1.1](#).

For the PP population, the results of the same proportion analysis on the number of subjects with anesthetic effect at 2 to 4 minutes post dose will be presented in [Table 2.1.2](#).

The by-site summary of descriptive statistics of the number of subjects with anesthetic effect at 2 to 4 minutes post dose will be presented in [Table 2.1.3](#).

The results of the proportion analysis on the number of subjects with anesthetic effect at 2 to 4 minutes post dose will be presented for the sub-populations of boys vs. girls in [Tables 2.2.1](#) and [2.2.2](#); for 8 years or younger vs. 9 years or older in [Tables 2.2.3](#) and [2.2.4](#); for Caucasian vs. Non-Caucasian in [Tables 2.2.5](#) and [2.2.6](#); and for iris color dark brown vs. other colors in [Tables 2.2.7](#) and [2.2.8](#).

Individual subjects' primary efficacy data (i.e., anesthetic effect) assessed post dose on Day 1 by Investigator, with and without imputation, will be listed by treatment for the ITT population ([Listing 6](#)).

### 4.5.2 Results of secondary efficacy analyses

There are no secondary efficacy endpoints defined in this study.

## 5 SAFETY EVALUATION

For safety evaluation, the safety population as defined in [Section 3.1](#) will be utilized to conduct safety analyses among treatment groups.

### 5.1 Extent of Drug Exposure

Exposure to study medication will be tabulated by treatment in [Table 3.1.1](#) for number of drops received, using the following categories: 1 drop and 2 drops. The tabulations will be done for the safety population, and for boys and girls, separately.

Individual subjects' treatment exposure (drops) will be listed by treatment for the safety population ([Listing 3](#)).

## 5.2 Early Termination

Early termination will be categorically summarized for the safety population in [Table 1.4.1](#), and for the ITT population in [Table 1.4.2](#). Subjects' study termination details will be listed ([Listing](#)

## 5.3 Adverse Events

An overall summary of AEs reported in this study will be provided in [Table 4.1.1](#) for study participants and in [Table 4.1.2](#) for the safety population. The incidences of subjects reporting pre-treatment AEs will be reported in [Table 4.2.1](#) for the pre-randomization period and in [Table 4.2.2](#) for the treatment-emergent AEs by treatment. Those treatment-emergent AEs by preferred terminology that are reported by more than 5% of subjects in any treatment will be tabulated in [Table 4.2.3](#).

Incidences of subjects reporting treatment-emergent AEs (TEAEs) will also be tabulated by treatment for the TEAEs associated with the study eye in [Table 4.2.5](#) and for the TEAEs associated with fellow eye in [Table 4.2.6](#).

Incidences of subjects reporting treatment-emergent AEs will also be tabulated by onset time (on-dosing day vs. post-dosing day) in [Table 4.3.1](#) for all TEAEs, and in [Table 4.3.2](#) for the TEAEs associated with the study eye, and in [Table 4.3.3](#) for the TEAEs associated with the fellow eye.

The severity of the treatment-emergent AEs and the relationship to the investigational product will be summarized in [Table 4.4.1](#).

Treatment-emergent AEs associated with early terminations and serious AEs will be summarized by preferred term, respectively, in [Table 4.4.2](#) and [Table 4.4.3](#) for all TEAEs, in [Table 4.4.4](#) and [Table 4.4.5](#) for the TEAEs associated with the study eye, and in [Table 4.4.6](#) and [Table 4.4.7](#) for the TEAEs associated with the fellow eye.

Details of AEs associated with both study and fellow eyes will be listed for each subject ([Listing 7](#))

Details of AEs associated with early terminations will be listed for each subject ([Listing 8](#)). SAEs, including deaths, will be listed for each event ([Listing 9](#)).

Narratives will be presented for all deaths, non-fatal serious adverse events, and subjects withdrawn due to adverse events.

